3.4. Randomization and Blind

Randomization will be performed based on recruited clusters. Stata 15 was used for randomisation code generation. Twenty-two community health care centres (clusters) will be allocated to an experimental arm or a control arm with 1:1 ratio using permuted block randomisation method with block size of 4. Randomisation list will be generated by an independent statistician.

The study is single blinded, the participants from the either arm will not know the medical care provided by the opposite arm. The study investigators who are involved in recruitment, the laboratory staff, and the dose-adjusting investigator (who was not involved in participant care) will remain blinded, since all the study outcomes will occur and observed at maternity hospitals. The investigator involved in intervention

and the statistician was not blinded, as unbinding was required to carry out statistical procedures.

The fetus and birth defects observers were maternity hospital ultrasound department and neonatologists and do their work according to the usual protocol and the data of outcomes were retrieved from the medical records. Therefore, all outcome assessments will be masked. The trial statistician will also be blinded regarding the treatment code when he develops the statistical analysis plan and writes the statistical programmers, which will be validated and completed using dummy randomisation codes. The actual allocation will only be provided to the study team after lock of the database.

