3. STUDY DESIGN

3.1. Design

This is a definitive, single-blind cluster randomized controlled - superiority trial embedded within the primary care system to assess the real-world effectiveness of a package of tertiary interventions before and during gestation in reducing the incidence of fetus and birth defects compared with the standard usual perinatal care. We will

recruit prepare-for-pregnancy women and their husbands through the pre-pregnancy eugenics examination clinic. Blood samples will be collected for examining RBC folate concentrations at enrollment. According to the randomization plan, participants recruited from the same community health care centre (cluster) will receive the same intervention, and clusters allocated to the two arms will receive the standard care or a serious experimental care procedure. The methods and protocols for measuring the primary outcome and the secondary outcomes in the two arms will follow the same clinical routines.

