3.3. Interventions

Experimental interventions: usual care plus additional procedures

- Before conception:

Participants will be examined for serum and RBC folate concentrations at enrollment to identify those with insufficient RBC folate concentration (<400ng/mL). Based on reviewing of folate supplement status of from the participant-administered questionnaire, a trained nurse will call the participant to inform them the RBC folate concentration and folate metabolism ability evaluated by one's genotypes of MTHFR C677T variant, and provide individualized folic acid supplementary instructions to improve folate status before get pregnant. A second RBC folate test is booked.

- During gestation -- Green channels for confirmation of fetus defects and a following genetic and clinical consulting:

In the both arms, fetus and infants with screen positive of fetus defect(s) will be referred via a green channel to approach an authorized tertiary obstetric hospital to achieve timely further routine comprehensive assessments and confirmative diagnosis. Then the participants with established diagnosis of fetus defects will be referred to a multi-discipline paediatric expert team for a deep consultation about possible postnatal treatments in the future to avoid unnecessary abortions.

- **After delivery:**

The participants from the experimental arm will additionally provide timely referral to a prespecified team of pediatrician experts for timely medical treatment or scheduled follow-up.

Standard tertiary interventions of birth defects (control arm, usual care):

Couples eligible for reproductive policy are entitled to routine health cares including general health cares (health education, medical history inquiry, physical examinations, consulting guidance and pregnancy outcome follow-up) and medical examinations (laboratory examinations, virus screenings and image examinations). But nutrients status is not included in these examinations, such as folate, vitamin B12 and microelements, etc. Regular antenatal cares are required, such as deformity screening by ultrasound. Routine neonatal screenings are conducted to diagnose infant with birth defect(s) timely.

Intervention procedures of FOID study

	Experimental arm Procedures in addition to the usual care	Control arm Usual care
Before conception		
Preconception at enrollment	RBC folate test Inform and instruction about folic acid supplementation via phone interview	Routine physical examination and routine blood tests

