4. ANALYSIS POPULATIONS

4.1. Study Population Data Sets

Two study populations will be considered in the analysis as follows:

- **Intent-to-Treat (ITT) population**

ITT population will be defined as the pregnant women among preparing-for-pregnancy couples that were recruited since November 1, 2018, from the randomized clusters and finally get pregnant. Participants will be excluded from the ITT analysis if the primary outcome is missing, forming a modified ITT population (mITT).

- **Per protocol (PP) population**

PP population will only include participants who received the treatments according to the protocol. Specifically,

- Participants of the experimental group: will be considered non-compliant with the preconception intervention if their RBC folate levels do not reach the target level (400 ng/ml) at the 1st antenatal visit.
- Participants in the control group received the usual care only, no non-complaints will be defined.
- Participants in both groups who do not have RBC folate levels measured at the 1st antenatal visit will not be included in the PP population.

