9.2. Appendix 2. FOID Study variable list

Appendix 2.1 Intervention trial variable list

NO	variable	
Pre-pregnancy		
1	hospital card number	T
2	Recruited number	T
3	Recruited date	D
4	Female name	T
5	Female height	N
6	Female weight	N
7	Female age	N
8	Male name	T
9	Male height	N
10	Male weight	N
11	Male age	N
12	Tel No	T
13	Community (basis for grouping)	N
14	Nutrient Interventions	B (1=intervention 0=control)
Nutrient first test		
15	Nutrient first test date	D
16	Serum folate	N
17	Red blood cell folate	N
18	Serum ferritin	N
19	VD(Vitamin D)	N
20	HCY(homocysteine)	N
21	Vitamin B12	N
22	LDL low density lipoprotein cholesterol	N
23	HDL high density lipoprotein cholesterol	N
24	TG total cholesterol	N
25	TC triglyceride	N
26	FBG(fasting blood-glucose)	N
27	Genotyping (BHMT (rs3733890), CBS (rs2850144, rs2851391), FIGN (rs2119289), MTHFD1 (rs2236225), MTHFR (rs1801131, rs1801133, rs3737965), MRT (rs1805087, rs28372871, rs1131450), MTRR (rs1801394, rs326119), RFC1 (rs1051266), and SHMT (rs1979277))	B
28	Clinical information (see Table 3)	-
29	Insufficient serum folate	B
30	Insufficient RBC folate	B

	Nutrient repetition measurement	
29	Nutrient repetition measurement date	D
30	Serum folate	N
31	Red blood cell folate	N
32	HCY (Homocysteine)	N
	Pregnancy	
33	Ultrasound image screen in mid-gestation	T
34	Report detail (positive)	B
35	Confirm image diagnosis	T
36	Therapeutic plan	T
37	birth defect diagnosis	T
38	Clinical information (see Table 2)	-

Note: T, text variable; D, The date type; N, Continuous variable; B, binary variable.

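### SAP 3.4 claims that recruiters, laboratory staff and the dose-adjusting investigator stay blinded, but its reason concerns only outcome assessment and the cluster design does not secure the claim

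*SAP*

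**What the plan says.** On blinding, SAP 3.4 says: "The study investigators who are involved in recruitment, the laboratory staff, and the dose-adjusting investigator (who was not involved in participant care) will remain blinded". The sentence goes on to its only justification: "since all the study outcomes will occur and observed at maternity hospitals". The same section describes the investigator who delivers the intervention and the statistician as not blinded. It later says that the trial statistician is blinded while the SAP and programs are written, and then: "The actual allocation will only be provided to the study team after lock of the database".

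On allocation, 3.1 says that "participants recruited from the same community health care centre (cluster) will receive the same intervention". Section 3.4 allocates 22 centres 1:1. Section 4.1 defines the ITT population as women "recruited since November 1, 2018, from the randomized clusters and finally get pregnant".

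On what differs between arms before conception, the table in 3.3 lists this in the experimental column only: "RBC folate test Inform and instruction about folic acid supplementation via phone interview". The text of 3.3 adds a nurse's call and the booking of a second RBC folate test under the experimental interventions. Section 3.1, however, describes the first sample without restricting it to an arm: "Blood samples will be collected for examining RBC folate concentrations at enrollment".

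On analysis, the main conclusion comes from a GEE with treatment as its only predictor (5.1.1).

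**The concern.** In a cluster trial that enrols individuals after the clusters are allocated, randomisation balances the centres. It does not balance which women each centre then approaches and enrols. Readers of such a trial therefore look for a statement about what recruiters knew. Section 3.4 gives a reassuring one, and a reader would use it to set recruitment bias aside.

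If that statement does not follow from the design, the reassurance is unearned. Any difference between arms in who was enrolled, or in who went on to conceive and so entered the ITT population, would pass directly into the unadjusted primary risk ratio.

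**Working it through.** The plan gives no figure on this point, so there is none to reproduce. The check sets the statements side by side, with two short calculations.

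**1. Claim against reason.** The claim covers people who act before conception or in the laboratory. The reason is that outcomes are observed elsewhere. That supports masking of the ultrasound departments and neonatologists who record outcomes. It says nothing about whether a centre's arm is visible to those recruiting in it. Section 3.4 names no other concealment measure for these roles.

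**2. Order of events.** Section 3.4 randomises recruited centres, and 4.1 describes women as recruited from centres already randomised. Enrolment therefore follows allocation.

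**3. Predictability.** Inputs: one arm per centre (3.1) and at least 111 women per centre (3.5). Given the centre's arm, P(next woman is in that arm) = 1. If the arm is recognised after the j-th woman, the remaining 111 − j assignments are known. For j = 1 this is 111 − 1 = 110.

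**4. What could reveal the arm.** The firm markers are the phone instruction and the booked second test, which 3.3 gives only as experimental procedures. Both follow a woman's own enrolment, but they can reveal the arm for women enrolled later at that centre. The first RBC folate test is not a firm marker. The 3.3 table puts it in one column, but 3.1 does not restrict it, and 5.1.2 and 5.1.3 use baseline RBC folate as a covariate and a subgroup variable across both arms.

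**5. Consistency within 3.4.**
- Allocation reaches the study team only after database lock, yet the intervention investigator is unblinded and must know which centres receive the intervention.
- The statistician is called not blinded in one paragraph and blinded in the next.

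**6. Exposure and existing checks.** The primary GEE has no baseline covariate (5.1.1). The SAP does plan the following:
- a flow chart of women screened, enrolled and followed up in each arm, with reasons for non-enrolment (6.2);
- a baseline table by arm (section 7, Table 1);
- a covariate-adjusted primary analysis with eight baseline covariates, including adverse pregnancy history and baseline RBC folate (5.1.2).

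Section 6.2 does not ask for enrolment or conception fractions, and asks for nothing by centre.

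**7. Does the planned adjustment work as written?** Section 5.1.2 fits a logistic propensity model with a random centre effect, but treatment is constant within each centre. For an intercept-only check, take 22 centres of 100 women, 11 per arm, with centre effect σu, u standard normal and φ its density. The intercept is 0 by symmetry and

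log-likelihood(σ) = 22 × ln ∫ [1/(1 + e^(−σu))]^100 φ(u) du.

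| σ | log-likelihood |
|---|---|
| 1 | −215 |
| 3 | −64 |
| 10 | −26 |
| limit as σ grows | 22 × ln 0.5 = −15.2 |

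The likelihood keeps rising towards a bound that it never reaches. The centre variance has no finite estimate, and centre-specific propensities go to 0 or 1. The analysis best placed to check differential recruitment therefore cannot be relied on in this form.

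**The case against.** The strongest reply is that nothing shows recruiters knew the arm. No section says they were told. The nurse who calls and the investigator who intervenes are described separately from those who recruit, and the call comes after enrolment. This stands: recruiter knowledge is an inference from the design. It does not rescue the claim, because 3.4 asserts blinding and offers no measure that would produce it.

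A second reply is that the SAP already checks for imbalance. A reader might infer that selective recruitment would go unnoticed. The documents do not support that, given the flow chart, the baseline table and the adjusted analysis. What remains is that disclosure does not correct an estimate, and that the one correction needs a workable model.

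A reader might also infer that laboratory staff and the dose-adjusting investigator cannot be blinded because they handle work from one arm only. The SAP does not show this. Sample coding is not described, the repeat-measurement variables in Appendix 2.1 are not limited to an arm, and the dose-adjusting role is described nowhere else. For these two roles the finding is only that the stated reason does not support the claim.

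Finally, the conflicts within 3.4 may have innocent explanations. The statistician may be blinded while programming and unblinded for analysis, or two people may be meant. Release after lock may refer to the analysis dataset. Either is plausible, but the text says neither.

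**Conclusion.** The point holds as a defect in what 3.4 asserts. Blinding of recruiters is not a property that this design secures, and the reason given does not support it for any of the three roles. The size that can be stated is predictability: probability 1 for every later woman at a centre once its arm is recognised. This rests on one arm per centre and on enrolment after allocation, both taken from the SAP.

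A reader might go further and conclude that the primary risk ratio is biased. The documents do not support that. They contain no information on how enrolment differed between arms, so no bias can be sized. RBC folate is first measured at enrolment and is not part of usual preconception care, so recruiters could not have selected on it directly. The risk is real, partly checked, and worth correcting in the SAP.

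**What to change.** **Section 3.4.** Withdraw the blinding claim for recruiters, laboratory staff and the dose-adjusting investigator, or state who recruits and which concealment measure supports it. State that allocation can be inferred at centre level after randomisation. Limit the masking claim to outcome assessors, which is where the stated reason belongs. Reconcile the two statements on the statistician, and say what is released after lock, to whom, and how this fits with an unblinded intervention investigator.

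**Section 6.2.** Extend the flow reporting to enrolled/screened and conceived/enrolled, by arm and by centre.

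**Section 5.1.2.** State that the primary risk ratio will be read alongside the covariate-adjusted analysis as the check on differential recruitment. Fit that analysis either as outcome regression within the GEE or with a propensity model that has no random centre effect.

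**Cost.** SAP wording, two extra fractions from screening, enrolment and pregnancy counts tabulated by centre, and a respecified version of an analysis already planned. No change to recruitment procedure is asked for, since 4.1 dates recruitment from November 2018. No individual data on non-enrolled women are needed.

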3.5. Sample Size

Sample size calculation was performed based on the primary outcome- the incidence of a composite rate of fetus, still birth, or birth defects. The proportion of primary endpoint was conservatively estimated to be 8% in the control arm according to two recent observational studies^{6,7} and 4% in the experimental arm (or 50% reduction) based on the findings of a meta-analysis of randomized intervention trials of folic acid supplementation intervention in folate-deficient population⁸. With cluster size of 100 subjects per centre, K coefficient of 0.23, a power of 85 % and a 5 % level of type I error, 22 clusters (2200 patients or 1100 in each arm) will be required. To allow for a 10 % dropout rate, at least 111 subjects (2446 patients or 1223 in each arm) will be recruited in each centre.

4. ANALYSIS POPULATIONS

4.1. Study Population Data Sets

Two study populations will be considered in the analysis as follows:

- **Intent-to-Treat (ITT) population**

ITT population will be defined as the pregnant women among preparing-for-pregnancy couples that were recruited since November 1, 2018, from the randomized clusters and finally get pregnant. Participants will be excluded from the ITT analysis if the primary outcome is missing, forming a modified ITT population (mITT).

- **Per protocol (PP) population**

PP population will only include participants who received the treatments according to the protocol. Specifically,

- Participants of the experimental group: will be considered non-compliant with the preconception intervention if their RBC folate levels do not reach the target level (400 ng/ml) at the 1st antenatal visit.
- Participants in the control group received the usual care only, no non-complaints will be defined.
- Participants in both groups who do not have RBC folate levels measured at the 1st antenatal visit will not be included in the PP population.

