1. INTRODUCTION

Birth defects are the main cause of fetal death, infant mortality, and morbidity worldwide. The protective effect of sufficient folic acid supplementations on several birth defects is well-established¹⁻³. However, most women failed to achieve the optimal folate status from diet alone⁴. We assume that achieving recommended folate levels before pregnancy through awareness of insufficient status and timely initiation of folic acid supplementation, based on the current red blood cell (RBC) folate status and genetic background of women of reproductive age, will exert an effect on primary prevention of both fetus and birth defects.

The FOID study is a single-blind, two-arm cluster-randomized controlled trial which conducted in Shanghai and Jiangsu Kunshan city, China⁵. This trial aims to evaluate the effectiveness of a comprehensive folate-oriented tertiary interventions (before pregnancy, during pregnancy and after delivery) embedded in the current routine primary care system in reducing the incidence of fetus and birth defects among a preparing-for-pregnancy population. The control arm will receive the current routine standard antenatal care interventions before pregnancy, while the experimental arm will additionally receive a folate-oriented tertiary intervention based on this. Before conception, the participants in the experimental arm will receive an RBC folate concentration test at enrollment, and those with insufficient levels (<400ng/mL) will receive a phone interview with an instruction of folic acid supplementation to improve their folate status to the target level before pregnancy based on a second RBC folate examination. During pregnancy, pregnancies with positive tests in the routine nuchal translucency (NT) screen at early gestation, ultrasound screening in mid-gestation will be referred to the authorized tertiary hospital for counseling according to their genetic and prenatal diagnosis of the fetal defect(s). After delivery, newborns with fetus and birth defect(s) will be referred to a clinical team at the authorized tertiary pediatric hospital for treatment and follow-up. The current pragmatic cluster randomized trial will provide real-world evidence on the necessity and effectiveness of preconception intervention focusing on achieving sufficient folate nutrition levels in prevention of

fetal and birth defects.

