5.1.2. Sensitivity analyses of the primary outcome

- **PP analysis of the primary outcome**

The same analysis of the primary outcome will be performed in the PP population using a GEE model (described in 5.1.1).

- **Covariate adjusted analysis of the primary outcome**

A GEE model used for the analysis of the primary outcome in Section 5.1.1 will also be used for covariate adjusted analysis using inverse probability of treatment weighting (IPTW) approach. The covariates will include age (continuous variable), ethnic (binary variable), body mass index (continuous variable), adverse pregnant history (binary variable), parity (continuous variable), exposure to smoking (mother or father's smoking status, binary variable), total cholesterol (continuous variable), and RBC folate level (continuous variable) at baseline to estimate adjusted risk ratio and 95% CI. Covariate adjusted analysis will be performed on both ITT and PP populations.

We will first calculate a propensity score with treatment as the dependent variable (1 for the experimental group and 0 for the reference group), and all covariates listed above as independent variables through a logistic regression model with a random effect for the center, and then perform an IPTW analysis (weighted GEE model). The adjusted risk ratio between the two groups and its two-sided 95%CI will be estimated.

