5.1.3. Subgroup analysis of the primary outcome

A GEE model used for the analysis of the primary outcome in Section 5.1.1 will also be used for subgroup analysis of the primary outcome.

Subgroup analyses will be performed on age (< or \geq 35), ethnic (Han ethnicity or other

ethnicities), BMI ($<$ or $\geq 24\text{kg}/\text{m}^2$), presence of adverse pregnant history (Yes, No), exposure to smoking (Yes, No), total cholesterol ($<$ or $\geq 5.2 \text{ mmol}/\text{L}$), RBC folate status at baseline ($<$ or $\geq 400 \text{ ng}/\text{mL}$). Subgroup analyses may also base on categorized variables of the above continuous variable based on median value to make sample sizes of the categories comparable to achieve greater power.

Assessment of the homogeneity of treatment effect by a subgroup variable will be conducted by a GEE with the treatment, subgroup variable, and their interaction term as predictors, center as cluster, and the *P*-value presented for the interaction term.

Subgroup analysis will be performed on both ITT and PP populations.

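### The per-protocol set drops experimental women below 400 ng/mL RBC folate at the first antenatal visit but no controls on level, which tilts it towards benefit

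*SAP*

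**What the plan says.** SAP 4.1 introduces the PP population as women treated as the protocol intends, and then sets three rules.

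- Experimental-arm women "will be considered non-compliant with the preconception intervention if their RBC folate levels do not reach the target level", which is 400 ng/mL, judged at the first antenatal visit.
- For controls: "Participants in the control group received the usual care only, no non-complaints will be defined".
- Women in either arm "who do not have RBC folate levels measured at the 1st antenatal visit will not be included in the PP population". This rule acts on missing values and not on level.

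The premise linking folate to the outcome is in section 1, which begins "We assume that achieving recommended folate levels before pregnancy" and goes on to expect prevention of fetal and birth defects.

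PP has three uses. Section 5.1.2 lists it first among the sensitivity analyses: "The same analysis of the primary outcome will be performed in the PP population using a GEE model". The same section reuses it for the weighted analysis ("Covariate adjusted analysis will be performed on both ITT and PP populations"), and section 5.1.3 does so for subgroups ("Subgroup analysis will be performed on both ITT and PP populations"). Section 5.1.1 draws the main conclusion from ITT.

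**The concern.** The rule measures response and not adherence. An experimental woman who had the test, took the call and followed the advice, but stayed below 400 ng/mL, is removed. A control with the same folate level stays in. This is selection on a post-randomisation value in one arm only. If low folate goes with higher risk, whether causally or through other factors, the experimental arm loses its higher-risk women and the control arm keeps its own.

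A sensitivity analysis should test whether the ITT result is robust. This one leans towards benefit by construction, so a PP estimate stronger than ITT could be read as confirmation when it reflects selection alone.

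**Working it through.** The SAP states no figure for the size of the PP set or its bias, so there is no planned number to reproduce.

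**Inputs from SAP 3.5:** control risk 8%; 22 clusters, so 11 per arm; 100 women per cluster; K = 0.23, taken here as the between-cluster coefficient of variation; 5% type I error, taken as two-sided.

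**Assumed, not in the SAP:** s, the share below 400 ng/mL at the first visit, and r, the risk ratio for low versus sufficient folate.

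**1. Null case.** Let the intervention have no effect and s be equal in both arms. Let p be the risk at sufficient folate.

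- Experimental PP risk = p
- Control PP risk = p(1 − s) + p·r·s = p(1 + s(r − 1))
- Expected PP risk ratio = 1/(1 + s(r − 1))

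Example with s = 0.3 and r = 2: p = 8%/1.3 = 6.15%, so the risk ratio is 6.15/8 = 0.77. A direct simulation of this case gave 1.00 for ITT and 0.77 for PP.

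| | s = 10% | s = 20% | s = 30% |
|---|---|---|---|
| r = 1 | 1.00 | 1.00 | 1.00 |
| r = 1.5 | 0.952 | 0.909 | 0.870 |
| r = 2 | 0.909 | 0.833 | 0.769 |

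**2. False significant benefit.** 20,000 null trials per scenario at the planned size, using the log risk ratio with cluster-robust variance and a t reference with 20 degrees of freedom:

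| | s = 10% | s = 20% | s = 30% |
|---|---|---|---|
| r = 1.5 | 4.4% | 6.8% | 9.5% |
| r = 2 | 7.1% | 14.5% | 23.8% |

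ITT gave 2.2% to 2.6% throughout, and PP at r = 1 gave 2.3% to 2.6%. A separate normal approximation, counting significance in either direction, gave 11.3% (r = 1.5) and 26.7% (r = 2) at s = 30%, against a nominal 5%.

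**3. Effective intervention.** If the intervention acts through folate and the experimental share below 400 ng/mL falls to s1, then PP risk ratio / ITT risk ratio = 1/(1 + s1(r − 1)). For s1 = 10% to 20% this is 0.95 to 0.91 at r = 1.5 and 0.91 to 0.83 at r = 2. Example with a control share of 40%, s1 = 20% and r = 2: ITT = 1.2/1.4 = 0.86 and PP = 1/1.4 = 0.71.

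**4. Does the planned weighting repair it?** The weights in section 5.1.2 use baseline covariates, including "RBC folate level (continuous variable) at baseline to estimate adjusted risk ratio and 95% CI". The check weighted on baseline log RBC folate in a very large sample, with s = 0.3, r = 2 and an assumed baseline to first-visit correlation:

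| Risk follows | Analysis | 0.3 | 0.5 | 0.7 | 0.9 |
|---|---|---|---|---|---|
| First-visit folate | Unadjusted | 0.769 | 0.769 | 0.769 | 0.769 |
| First-visit folate | Weighted | 0.773 | 0.780 | 0.791 | 0.806 |
| Baseline folate only | Unadjusted | 0.96 | 0.93 | 0.89 | – |
| Baseline folate only | Weighted | 1.00 | 0.99 | 0.97 | – |

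Weighting removes only the part of the selection that the baseline covariates explain.

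**5. Residual bias of a receipt-based rule.** Let b be the share below 400 ng/mL at enrolment and u the share of those women without documented receipt, with risk following enrolment status. The null risk ratio is [((1 − b) + b(1 − u)r)/(1 − bu)] / (1 + b(r − 1)). Example with b = 0.5, u = 0.2 and r = 2: (1.3/0.9)/1.5 = 0.96.

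| b = 20% to 50% | r = 1.5 | r = 2 |
|---|---|---|
| u = 10% to 20% | 0.98 to 0.99 | 0.96 to 0.99 |
| u = 50% | 0.93 to 0.96 | 0.89 to 0.93 |

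**6. First-visit measurement in controls.** Section 4.1 and Table 2 in section 7 presume a first-visit RBC folate value in both arms. The procedures table in section 3.3 lists that test in the experimental column only, and the routine antenatal list in Appendix 2.2 has serum folate only. This does not show that controls are untested. The same table also places the enrolment test in the experimental column only, although section 3.1 states it with no arm limit, and Appendix 2.1 has a repeat RBC folate block.

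**The case against.** **PP decides nothing.** ITT carries the conclusion and no decision rule uses PP, so false-significance rates overstate the stakes. The premise is correct and limits the severity. It does not rescue PP as a check on robustness.

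**The size is assumed.** With r = 1.25 and s = 10% to 20%, the null risk ratio is only 0.98 to 0.95. The composite covers 24 defect types, including trisomy 21 and an open category for others, so the link with folate may be weak. This stands: the direction is firm for any r above 1, but the size is not.

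**The null scenario is harsh.** It supposes that the intervention shifts folate in no one on balance and that risk follows first-visit status fully. If risk follows baseline folate only, the unadjusted bias is smaller and weighting removes most of it. The truth may lie between. However, the SAP also plans PP unweighted, and step 3 shows that an overstatement remains when the intervention works.

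**It may be a different estimand.** If the folate effect is causal and unconfounded, the comparison describes full target attainment against usual care. That is a fair reading, but it is not what section 4.1 announces, and it needs a no-confounding assumption that the SAP does not state.

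**Receipt may be hard to derive.** Appendix 2 lists no variable for the phone call. Section 3.3 says only that a second test is booked, whereas a repeat-test date shows attendance. If non-receivers also carried 1.5 times the risk, with b = 50%, u = 20% and r = 2, the receipt rule would give 0.90, close to the 0.91 of the current rule at s = 10%. That comparison pairs a large b with a small s, but the difficulty is real and the fix needs a fallback.

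**Conclusion.** The concern holds. The PP definition selects on an attained post-randomisation folate level in one arm, and the bias runs towards benefit whenever low folate marks higher risk. For assumed shares of 10% to 30% below 400 ng/mL, the expected null PP risk ratio is 0.95 to 0.87 at r = 1.5 and 0.91 to 0.77 at r = 2. The chance of a false significant benefit rises from about 2.5% to between 4% and 24%. These sizes rest on assumed s and r, equal s in both arms, risk following first-visit folate, and K read as a coefficient of variation. The asymmetry itself needs no assumption. ITT is untouched, so this should be fixed but does not threaten the main conclusion.

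**What to change.** 1. In section 4.1, delete the attained-folate exclusion and the first-visit measurement requirement that serves it.
2. Define experimental-arm PP by documented receipt of the preconception components in section 3.3: the enrolment RBC folate test and, where the result was below 400 ng/mL, the phone instruction and the booked second test. Take receipt from call records if they are kept. Otherwise use the repeat-measurement date in Appendix 2.1 (the date and not the value), after confirming that this block records the preconception second test.
3. State that, apart from women with no enrolment test, this rule still excludes only women with low enrolment folate and only from one arm. A smaller bias towards benefit therefore remains, and the PP estimate should be read together with the version adjusted for baseline RBC folate.
4. If receipt cannot be derived, keep the attained-folate comparison as exploratory only, state that its bias runs towards benefit, and remove it from the sensitivity analyses of the primary outcome.
5. Clarify in one line whether controls have a first-visit RBC folate value, reconciling the procedures table and Appendix 2.2 with section 4.1, Table 2 and Appendix 2.1.

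Applying the 400 ng/mL rule to both arms is not a good substitute. It returns the null risk ratio to 1.00, but it conditions on the pathway through which the intervention is meant to act and would hide an effect through folate.

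The cost is SAP wording, a records check and one re-derived flag. The PP estimate may be less favourable and closer to ITT, and it will describe delivery of the components and not whether supplements were taken.
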